## **IX. Adverse Event Reporting:**

The University of Iowa requires Investigators to collect and report to the University of Iowa IRB if any of the following occur:

- An unanticipated problem involving risks to subjects or others is any event or problem that:
  - 1) was unexpected (in terms of nature, severity or frequency) given (a) the research procedures that are described in the protocol-related documents, such as the IRB- approved research protocol and informed consent document; and (b) the characteristics of the subject population being studied AND
  - 2) suggests that the research places subjects or others (those not directly involved in the research such as research staff or family members) at a greater risk of harm (including physical, psychological, economic, or social harm) than was previously known or recognized AND
  - 3) is related or possibly related to participation in the research (possibly related means there is a reasonable possibility that the incident, experience or outcome may have been caused by the procedures involved in the research).
  - 4) Serious adverse drug event (either expected or unexpected) occurring in a UI subject
  - 5) If a subject is enrolled by U/VAHCS investigators, the investigator must report to the UI IRB either serious adverse drug events or unexpected adverse drug events. By definition, these events must be associated with the use of the drug.
  - 6) An unexpected adverse drug event is any adverse drug experience (associated with the use of the drug), the frequency, specificity, or severity of which is not consistent with the current investigator brochure; or, if an investigator brochure is not required or available, the specificity or severity of which is not consistent with the risk information provided to the subjects and the IRB
- A serious adverse drug event is any adverse drug experience (associated with the use of the drug) occurring at any dose that results in any of the following outcomes:
  - 1) Death

- 2) Life-threatening adverse drug experience
- 3) Inpatient hospitalization or prolongation of existing hospitalization
- 4) A persistent or significant disability/incapacity
- 5) A congenital anomaly/birth defect
- 6) Important medical events that may not result in death, be life-threatening, or require hospitalization may be considered a serious adverse drug event when, based upon appropriate medical judgment, they may jeopardize the patient or subject and may require medical or surgical intervention to prevent one of the outcomes listed above.

- Receipt of new information

During the course of a study, researchers may become aware of new information that would impact a subject's decision to participate or continue participating in the research study. For example, interim analyses of data may identify a trend which impacts the safety of subjects or may identify early efficacy (benefit) of one of the interventions under study. In addition, results from other research studies or changes in standards of practice or care may affect conduct of a study and would need to be communicated to research subjects.
- Noncompliance

Noncompliance is a failure to follow the federal regulations with respect to protection of human subjects in research or failure to follow the determinations of the IRB with respect to conduct of the research as approved by the IRB.

Once per year, the IRB is required to review and approve all non-exempt research projects at intervals appropriate to the degree of risk, but not less than once a year. This is called "continuing review." Continuing review for non-exempt research is required to occur as long as the research remains active for long-term follow-up of the research subject, even when the research is permanently closed to the enrollment of new subjects and all subjects have completed all research-related interventions and to occur when the remaining research activities are limited to collection of private identifiable information.

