## VIII. Study Procedures

After informative consent signed by potential subject and at the same visit (initial visit), every subject will undergo pacemaker/defibrillator screening check, transthoracic echocardiogram if no echocardiogram available within 6 months preceding the initial visit, and pregnancy test for females whose age 18-50 year-old, if subject is deemed still eligible based on the results of this initial visit screening tests, he/she will be randomized to one of the study's arm and undergo the following baseline tests/procedures.

Initial visit baseline tests/procedures:

A- 6-minute walking test if subject has not had one within 3 months prior to enrollment.

B- Subject will be requested to fill two questionnaires:

- 1- "Minnesota living with heart failure" questionnaire to assess your quality of life
- 2- "Self-assigned New York Heart Association survey (SA-NYHA)" to evaluate the severity of your heart failure symptoms.

C- Medications review, vital signs (heart rate, blood pressure measurement, and weight)

D Baseline pre- and post-programming 12 leads EKG

E- Pacemaker/defibrillator programming session will be performed on all subjects.

Patient assigned to the arm that start with pacing initial treatment period, their devices will be programmed according to our study protocol for RBBB pacing therapy.

After the initial visit, subject will be scheduled for follow up visits. Each visit will last approximately (60-120 minutes) and will be located at University of Iowa Heart and Vascular center –adult outpatient facilities where each subject will have the following tests performed:

A-Follow up trans-thoracic echocardiogram

B-Follow up 6-minute walking test

C-Subject will be requested to fill the two-questionnaire mentioned above again for follow up purposes.

D-Medications review, follow up vital signs (heart rate, blood pressure measurement, and weight)

E-Subject will be asked whether has been hospitalized, has had any medication changes, or has suffered any acute myocardial infarction or stroke/TIA for the preceding 3 months.

F- Blood draw for laboratory tests (Sodium, BUN, Cr, and NT-proBNP)

G-Baseline pre- and post-programming 12 leads EKG

H-Follow up pacemaker/defibrillator check

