#### **Adverse Event Collection:**

The clinical research team is responsible for collecting and recording the research data. As the results are collected, all adverse events will be identified after an informed consent is signed by the subject.

Throughout the study, during all follow-up visits, in addition to the medical chart review, adverse events are to be elicited by the investigator (or designate) by asking the subject

non-leading questions. All AEs and SAEs will be reported to the principal investigator (PI) and the PI will determine the final relationship of the event to the investigational product.

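### In a device-programming trial, section IX defines serious events, and requires IRB reports of expected ones, only as drug events; the fixed look-back at week 20 also re-asks about period 1

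*Protocol*

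**What the plan says.** **Intervention.** Section VIII says of subjects who start with pacing that "their devices will be programmed according to our study protocol for RBBB pacing therapy". No drug is under study.

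**IRB reporting.** Section IX lists what must go to the University of Iowa IRB. One item is an unanticipated problem, which must meet three tests joined by AND. The event "was unexpected (in terms of nature, severity or frequency) given" the research procedures and the population; it suggests greater risk than was known; and it is related or possibly related to the research. Another item is "Serious adverse drug event (either expected or unexpected) occurring in a UI subject". The seriousness definition then begins "A serious adverse drug event is any adverse drug experience (associated with the use of the drug) occurring at any dose" and continues with the usual outcomes, from death to important medical events. For subjects enrolled by U/VAHCS investigators the section adds "By definition, these events must be associated with the use of the drug". New information is also reportable, for example where "interim analyses of data may identify a trend which impacts the safety of subjects".

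**Collection.** The Adverse Event Collection subsection sends all AEs and SAEs to the principal investigator, who decides their relationship to the investigational product. It also says that "in addition to the medical chart review, adverse events are to be elicited by the investigator" or a designate, at all follow-up visits.

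**Event question.** Section VIII, follow-up item E, asks at each follow-up visit about hospitalisation, medication changes, myocardial infarction and stroke or TIA over the previous three months. Section I sets two 12-week periods with an 8-week washout between them, and visits at baseline and weeks 12, 20 and 32.

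**The concern.** A rule that applies only to drug events cannot be triggered where nothing is dosed. The drug item is also the only serious-event item in section IX that covers expected events. In this trial, the serious events most likely to bear on whether pacing is safe may well be expected ones, such as heart-failure admissions in patients with an ejection fraction of 35% or less. If no explicit rule covers them, whether such an event is reported depends on case-by-case judgement about unexpectedness or new information.

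The event question raises a separate, smaller matter. In a crossover, a safety listing is interpretable only if each event can be placed under the device setting in force when it occurred. A fixed three-month window does not match an 8-week washout.

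**Working it through.** **Part 1: follow one event through section IX.** Take a heart-failure admission during a paced period that the investigator thinks pacing may have contributed to. Assume that it counts as expected in this population; the consent form, which also bears on expectedness, was not supplied.

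| Route | Does it apply? |
|---|---|
| Serious-event item | No. It is confined to drug events, although it covers expected ones. |
| Unanticipated problem | Not by nature, because the event is expected. It could apply if its frequency or severity were judged unexpected and greater risk were suggested. |
| New information | Possibly, if a trend is noticed and judged relevant to participation. |
| Report to the principal investigator | Yes. But SAE has no definition except the drug one, and this is not an IRB report. |

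If the event is unexpected, suggests greater risk and is possibly related, the second route applies, and nothing limits it to drugs. The gap is therefore the expected serious event associated with pacing.

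A word count agrees with this reading. Section IX, including Adverse Event Collection, uses the word drug 12 times. Device, pacemaker, defibrillator, pacing and programming occur 0 times. The neutral term investigational product appears in Adverse Event Collection, but only for the relatedness decision.

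**Part 2: the look-back.** Inputs from section I: period 1 is weeks 0 to 12, washout is weeks 12 to 20, and period 2 is weeks 20 to 32. Let L be three months in weeks. The plan does not fix L, so 12 and 13 are both shown.

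- Week-20 window: from week 20 − L to week 20.
- Part of it in period 1: 12 − (20 − L) = L − 8 weeks.
- L = 12: 12 − 8 = 4 weeks, which is 4/12 = 33% of the window and 4/12 = 33% of period 1.
- L = 13: 13 − 8 = 5 weeks, which is 5/13 = 38% of the window and 5/12 = 42% of period 1.
- Week-12 and week-32 windows: each reaches L − 12 = 0 to 1 week before its own period.

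In person-weeks, assuming 40 subjects, 20 per sequence and full attendance, 20 × 4 = 80 to 20 × 5 = 100 paced person-weeks are asked about again at week 20. The same number of non-paced person-weeks is asked about again.

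If the question ran from the last visit, the windows would be 12, 8 and 12 weeks. These sum to 32, with no overlap and no boundary crossed.

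**The case against.** **Serious pacing events are still reportable.** A reader might infer from the drug wording that no serious pacing event has to reach the IRB. The documents do not support that. The unanticipated-problem route covers events of any kind and tests relatedness to the research procedures. The principal investigator also receives all AEs and SAEs. This objection stands, and it confines the point to expected events.

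**Drug reporting would not be automatic either.** A reader might suppose that a drug trial under this text would report every expected serious event. It would not, because the drug definition itself requires association with the drug. The fair comparison is between an expected serious event associated with a drug, which has a rule, and one associated with pacing, which has none.

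**Other text may govern.** Section III commits the study to Good Clinical Practice and applicable FDA requirements. That weakens any claim that section IX is the only rule, but it supplies no definition. By the contents list, the sections missing from the supplied text are IV (IRB Oversight) and V (Location of Study Procedures), and what they say cannot be judged.

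**Section IX restates university policy.** One protocol cannot rewrite that policy. This stands, and it shapes the fix: add a trial-specific rule alongside it.

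**The look-back loses nothing.** The week-12 visit already covers period 1, and chart review can supply dates. The overlap is the same in both sequences, so it does not by itself favour either setting. The case report forms were not supplied, so it cannot be said that dates go unrecorded. A reader might go further and claim that washout events would be overstated by 12/8 = 1.5 to 13/8 = 1.63 times. That requires a constant event rate and week-20 answers listed as washout without re-dating. Neither document plans such a listing, and the SAP contains no safety analysis.

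**Conclusion.** The point holds in its narrow form and is minor. In the supplied text, an expected serious event associated with pacing has no seriousness definition and no explicit IRB rule, whereas an expected serious drug event has both. This part has no numerical size. It rests on section IX as written and on treating the drug items as separate entries, although their numbering runs on from the unanticipated-problem tests.

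The secondary point is a 4- to 5-week overlap at week 20, depending on whether three months means 12 or 13 weeks. The overlap measures how far the question reaches back and does not count misclassified events. It creates a small risk of duplicate or misdated events. Efficacy conclusions are untouched.

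**What to change.** 1. Add to section IX a trial-specific definition of a serious adverse event. Keep the existing outcome list, drop the references to drug and dose, and apply it to any event after consent. SAE in Adverse Event Collection then has a usable meaning.
2. Add a trial-specific rule, alongside the university's list, to report to the IRB any serious event, expected or unexpected, that is associated or possibly associated with the device, its leads or its programming.
3. In section VIII, follow-up item E, ask about the time since the last visit and record the date of each event.
4. List AEs, SAEs and hospitalisations by device setting at the event date (paced, non-paced, washout), descriptively and without tests. Numbers this small would not support more: even 0 of 40 subjects with an event leaves an exact upper 95% limit of 1 − 0.025^(1/40) = 8.8%, if all 40 contribute data under that setting.

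The cost is some edited wording, one date field, one descriptive table and perhaps a few more IRB reports. No visit or test is added.

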#### **Adverse Event Collection:**

The clinical research team is responsible for collecting and recording the research data. As the results are collected, all adverse events will be identified after an informed consent is signed by the subject.

Throughout the study, during all follow-up visits, in addition to the medical chart review, adverse events are to be elicited by the investigator (or designate) by asking the subject

non-leading questions. All AEs and SAEs will be reported to the principal investigator (PI) and the PI will determine the final relationship of the event to the investigational product.

## X. Data Management

The following people/agencies may have access to subject data/records:

- Study team
- Federal government regulatory agencies
- Auditing departments of the University of Iowa
- The National Institute of Health

To protect confidentiality, we will assign each subject a study ID. All records will be in a locked cabinet in a locked office or password protected computer system. Data and records will be managed as follows:

- Paper/hard copy records (hard copy surveys, questionnaires, case report forms, pictures, etc.) - Whenever possible, subject identifying information will be blacked out on all paper or hard copy records and replaced with the subject's unique study identifier. Paper records will be stored in a locked file cabinet in the study team's locked office.
- Electronic records (computer files, electronic databases, etc.) – All electronic data bases will only be accessed by the study team and available only with a username and password assigned to study team by the PI.

## **XI. Subject Safety**

- To minimize risks all subjects are carefully pre-screened and screened trying to identify any factors that could contribute to increased risk.
- All testing is completed at University of Iowa Hospitals and Clinics by a very experienced and well-trained staff and monitored by the Principal Investigator.
- All confidential information is kept in locked offices and password protected computers only available to study team members.
- The participant has contact information and study team members available 24/7.

Cover Page for Statistical Analysis Plan

Sponsor-Investigator:	[name]
NCT Number:	NCT02441101
Unique Protocol ID:	201409760
Official Title:	Right Ventricular Septal Pacing in Patients With Right Bundle Branch Block and Heart Failure (The SPARK Trial)
Date of Document:	24 December 2014

Linear mixed model analysis for repeated measures will be used to test for change over the follow-up period in the primary outcome measures. Post-hoc pairwise comparison with baseline will be performed using Dunnett's test. Mean estimates at each time point, and mean change from baseline (with 95% confidence limits) will be computed from the fitted model. All tests were two-tailed and a $p < 0.05$ was considered as statistically significant. All analyses will be conducted using the intention-to-treat population.

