Our study's design is a randomized controlled single blinded cross-over study. Overall designs will include two 12 weeks treatment periods separated by 8 weeks washout periods.

One group will have pacing-washout-placebo sequence while the other will have placebo-washout-pacing sequence. Subjects will be randomized to either pacing (intervention) or non-pacing (placebo) with 1:1 ratio at the initial visit. Each subject will undergo heart ultrasound (echocardiogram), symptoms/quality of life assessment, and 6 minute walking distance assessment at initial, 12, 20, 32 weeks visits. This type of clinical trial design will have an advantage of blinding the intervention to the subject which will minimize bias and would create a control group. Indeed, will allow still to use relatively small number of subjects with enough power to test outcomes comparable to single arm prospective trial design, while parallel randomized controlled studies design would require higher subjects numbers for reaching an adequate power to test outcomes of interest due to lack of self control.

This study will allow us to evaluate the effect of this intervention on heart failure symptoms, heart size and function as well as quality of life in this specific group of heart failure patients.

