## **VII. Inclusion Criteria**

Our subject population is one group of patients who has the diagnosis of systolic heart failure.

Inclusion criteria:

Cardiomyopathy, ischemic or non-ischemic on optimal medical therapy per current heart failure treatment guidelines for at least 3 months.

LVEF <=35% by echocardiogram

Prior implantation of pacemaker/defibrillator with at least atrial and RV mid septal leads. Atrial lead can be waived if RV lead has atrial sensing capabilities.

Presence of right bundle branch block (RBBB), with QRS duration =>120 msec

Normal sinus rhythm

PR interval <250 msec on surface EKG

-Note: Subjects with Biventricular pacemaker/ICD will be enrolled if their LV lead has been deactivated by the their primary cardiologist prior to study enrollment for at least 3 months (this could be due to lead malfunction or the decision to deactivate the biventricular pacing therapy for any reason per primary cardiologist discretion)

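### The SAP tests change over time and against baseline, but no stated test compares pacing with non-pacing in this randomised cross-over

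*SAP*

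**What the plan says.** **Design (Protocol, I. Introduction).** The trial is a single-blind, two-period cross-over: two 12-week periods, an 8-week washout, and two sequences (pacing first or non-pacing first). Allocation is stated as: "Subjects will be randomized to either pacing (intervention) or non-pacing (placebo) with 1:1 ratio at the initial visit". The design is justified partly by "blinding the intervention to the subject which will minimize bias and would create a control group". On assessments: "Each subject will undergo heart ultrasound (echocardiogram), symptoms/quality of life assessment, and 6 minute walking distance assessment at initial, 12, 20, 32 weeks visits".

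**Analysis (SAP, a single paragraph).** The main test is: "Linear mixed model analysis for repeated measures will be used to test for change over the follow-up period in the primary outcome measures". Then: "Post-hoc pairwise comparison with baseline will be performed using" Dunnett's test. The estimates are: "Mean estimates at each time point, and mean change from baseline", with 95% limits. Tests are two-sided at 0.05 in the intention-to-treat population. The fixed and random effects are not listed, and baseline is not defined.

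**Elsewhere.** The Protocol has no statistics section. Its sections IV and V were not available for this check. By the contents list they cover IRB oversight and the location of procedures, so analysis text there is unlikely.

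**Baseline echocardiogram.** VII. Inclusion Criteria requires "LVEF <=35% by echocardiogram". VIII. Study Procedures asks at the initial visit for a "transthoracic echocardiogram if no echocardiogram available within 6 months preceding the initial visit", whereas the Introduction schedules one at that visit for every subject.

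**The concern.** The wording of the SAP would suit a single-arm before-and-after study. The question the randomisation was set up to answer, whether LVEF after a pacing period differs from LVEF after a non-pacing period in the same patients, is not among the stated tests.

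Two consequences follow, depending on what the undefined model factor is:

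- **Visit.** At weeks 12 and 32 half the subjects have just been paced and half have not. The visit mean therefore holds only half of any pacing effect, and power falls.
- **Treatment phase** (baseline, pacing, washout, non-pacing). Power is kept, and the non-pacing phase does enter the overall test. But the Dunnett step still sets pacing against baseline, so the estimated change is the pacing effect plus whatever else changed after baseline.

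Under either coding, a general rise in LVEF after baseline can give a significant result when pacing does nothing. Such a rise is possible, not established. One route lies in the Protocol itself: if the echocardiogram that qualified a subject at or below 35% is also used as baseline, regression to the mean will lift the later values. The requirement of at least 3 months of prior optimal therapy does not remove that route.

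**Working it through.** The SAP gives no power figure to reproduce. The Protocol gives 40 subjects, but no effect size, SD or dropout. The calculation below is therefore an illustration.

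**Inputs from the documents:** n = 40; 1:1 allocation; weeks 0, 12, 20, 32; two-sided 0.05; LVEF limit 35%.

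**Assumed:** 20 per sequence; no carry-over or dropout; within-subject LVEF SD σ = 4 points (range 3 to 6); true pacing effect δ = 4 points (also 2).

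**Step 1. What each analysis estimates.** With a common change τ after baseline, the week-12 mean change is τ + (20δ + 20·0)/40 = τ + δ/2. The pacing-phase change is τ + δ. The cross-over contrast is half the between-sequence difference in week 12 minus week 32. It estimates δ, because any change common to both sequences cancels.

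**Step 2. Power, no common change (τ = 0).**

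- *Cross-over contrast:* SE = σ·√2·√(1/20 + 1/20)/2 = 4 × 1.414 × 0.316/2 = 0.894. Noncentrality 4/0.894 = 4.47 on 38 df gives 99.2%. At σ = 6, SE = 1.342 and power is 82.8%.
- *Visit factor, overall F on 3 and 117 df:* visit means are 0, 2, 0, 2, with squared deviations summing to 4. Mixing paced and unpaced subjects also inflates the residual mean square: 16 + 40 × (2² + 2²)/117 = 18.7. Noncentrality is about 40 × 4/18.7 = 8.5. Simulated power is 66%.
- *Phase factor, overall F:* means are 0, 4, 0, 0, with squared deviations summing to 12. Noncentrality 40 × 12/16 = 30; power 99.8%.
- *Dunnett:* critical value 2.380 (three comparisons, 117 df).

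| Test, δ = 4 | σ = 3 | σ = 4 | σ = 6 |
|---|---|---|---|
| Visit, overall | 89% | 66% | 34% |
| Visit, any Dunnett | 77% | 53% | 28% |
| Phase, overall | 100% | 99.8% | 87% |
| Phase, Dunnett pacing vs baseline | 100% | 98% | 73% |
| Cross-over contrast | 100% | 99% | 83% |

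For δ = 2 at σ = 4: visit overall 21%, phase overall 61%, pacing vs baseline 44%, contrast 59%.

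**Step 3. False positives with no pacing effect.** Take regression to the mean as the only source of a rise, with between-subject SD 6 and σ = 4. The total SD is √(36 + 16) = 7.21. If the qualifying echocardiogram is the baseline, the expected rise is (16/7.21)·φ(z)/Φ(z), with z = (35 − source mean)/7.21. For source means 28, 32 and 35:

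- z = 0.97: 2.219 × 0.2491/0.8342 = 0.66
- z = 0.42: 2.219 × 0.3659/0.6613 = 1.23
- z = 0: 2.219 × 0.3989/0.5 = 1.77

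| Baseline is the qualifying echo for | Overall test significant (means 28, 32, 35) | Pacing significantly above baseline |
|---|---|---|
| All subjects | 10%, 26%, 52% | 5%, 16%, 36% |
| Half | 6%, 9%, 14% | 2%, 5%, 9% |
| None (fresh echo for all) | 5% | 1% |

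The last column counts the benefit direction only. With all qualifying echoes re-used, the overall test rejects in 8%, 16%, 34% of trials at σ = 3 and 18%, 47%, 79% at σ = 6. The cross-over contrast stays at about 5% in every case.

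**Step 4. A cause-neutral check.** A separate simulation (σ = 5, no pacing effect) gave every follow-up visit a common rise of 2, 3 or 5 points, whatever the reason. The visit-coded overall test rejected in 41%, 78% and 99.8% of trials, and the cross-over contrast in about 5%.

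**The case against.** The SAP is silent on model terms; it does not exclude them. A linear mixed model can carry treatment, period and sequence, and other readings are open, such as a separate baseline for each period (weeks 0 and 20) or means by sequence and visit. With period-specific baselines, half of the pacing changes would start from week 20, which weakens the regression-to-the-mean argument. The power loss belongs to the pooled visit reading alone; under phase coding the overall test does as well as the contrast. The largest false-positive rates need every qualifying echocardiogram to be re-used and a source mean at the eligibility limit. If every subject has an echocardiogram at the initial visit, as the Introduction schedules, there is no inflation from this route. Finally, the stated primary endpoint (Protocol VI) is a responder definition, while the calculations concern mean LVEF.

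Much of this stands as a limit on the figures: they are conditional and secondary. It does not answer the main point. A period-specific baseline is still a comparison with baseline, and no reading of the text turns a stated test into pacing against non-pacing. Working with mean LVEF follows the SAP's own choice of a linear mixed model. Pilot status helps little, because the Introduction claims adequate power and the Background (section II) looks to the result to support a larger trial.

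**Conclusion.** The concern holds and needs correcting before analysis. That the randomised comparison is missing from the stated analysis rests on the text alone and on no assumed number.

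The size of the consequence does depend on assumptions. If the factor is visit, the effect in the end-of-period means is halved, and power for 4 points at σ = 4 is 66% (overall) or 53% (Dunnett), against 99% for the contrast. If it is treatment phase, there is little or no power loss and the harm is one of attribution. The false-positive rate of the overall test from regression to the mean runs from no inflation (5%) with fresh baseline echocardiograms to 52% in the least favourable σ = 4 case. The SDs, the source means and the share of re-used echocardiograms are all assumed.

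**What to change.** **Primary analysis.** Fit a mixed model to the end-of-period values (weeks 12 and 32), with treatment, period and sequence as fixed effects and subject as random. The primary test is pacing minus non-pacing, two-sided 0.05, with estimate and 95% CI. State in advance how weeks 0 and 20 are used. Keep changes from baseline as description.

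**Supporting analyses.**

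- Carry-over: report the between-sequence difference in week-20 minus week-0 change with its CI, and do not let it choose the analysis. At σ = 4 the half-width is 2.024 × 4 × √2 × √0.1 = 3.6 points, so it cannot rule carry-over out.
- Sensitivity: compare the sequences at week 12, adjusted for week 0. At σ = 4 and between-subject SD 6 the correlation is 36/52, the SE is 7.21 × √(1 − 0.692²) × √0.1 = 1.65, and power for 4 points is about 66% (86% at σ = 3, 39% at σ = 6).

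**Definitions.** State which echocardiogram is the baseline, reconciling the Introduction with section VIII. Tie the section VI endpoint, set at 6 months (none of weeks 0, 12, 20 or 32), to the end-of-period visits. If the responder definition of more than 15% is kept, compare it between conditions within subject.

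**Cost.** Text changes to the SAP, the section VI time point and one line on the baseline echocardiogram. The endpoint timing is a real change and should be recorded as such. No patients, visits or data are needed beyond those the Introduction already schedules.
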